6 STUDY DRUGS

6.1 Overview of Study Drugs

6.1.1 Drug information

- **SHR-1210:**

Name: SHR-1210 for injection

Manufacturer: Shanghai Hengrui Pharmaceutical Co., Ltd./Suzhou Suncadia Biopharmaceuticals Co., Ltd.

Dosage Form: Lyophilized powder for injection

Route of Administration: Intravenous injection

Strength: 200 mg/20 mL vial.

Storage and stability: Placed in a 2-8 °C medical refrigerator during storage and the shelf life is tentatively set to 2 years. Do not freeze.

- **Apatinib:**

Name: Apatinib Mesylate Tablets (Apatinib)

Manufacturer: Jiangsu Hengrui Pharmaceuticals Co., Ltd.

Dosage Form: Tablets

Route of Administration: Oral

Strength: 250 mg/tablet; 375 mg/tablet

Storage and Stability: Away from light, sealed, stored at below 25 °C. Valid for 2 years.

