During the study, in the case of Grade ≥ 3 immune-related pneumonitis, Grade ≥ 3 TBIL elevation (recurrent), Grade 4 ALT/AST elevation (recurrent), other Grade 4 immune-related toxicities (except for hypothyroidism), Grade 4 injection reactions, or the interruption of SHR-1210 administration for more than 12 weeks due to immune-related toxicity but the toxicity is still unable to return to Grade ≤ 1 or baseline levels (subjects with baseline abnormality), SHR-1210 should be permanently discontinued.

After discontinuation of SHR-1210 treatment, subjects may continue to receive apatinib monotherapy after toxicity recovery if the investigator judges that the subjects can benefit from the apatinib monotherapy, until an event meeting the criteria for discontinuation as specified in the protocol occurs.

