8.6 Infusion Reactions

During the course of this study, the investigator should pay close attention to potential infusion and/or allergic reactions, especially acute immune-mediated adverse reactions (including cytokine storms).

Generally, there is no need for prophylactics before infusion of SHR-1210. Based on published relevant information, an allergic reaction/event is most likely to occur within 24 h after infusion. If an allergic reaction/event occurs, the infusion should be slowed or interrupted according to the situation, and a supportive treatment should be given. In addition, prophylactics should be given before further administration. Possible allergic reactions include fever, chills, shiver, headache, rash, pruritus, joint pain, hypotension/hypertension, or bronchospasm. All Grade 3 or 4 infusion reactions should be reported in accordance with SAE reporting procedures.

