9.2 Infusion Reactions

As a fully humanized monoclonal antibody, SHR-1210 poses relatively lower risks of infusion reactions and prophylactic is therefore not required. Once an infusion reaction occurs, the infusion should be slowed or interrupted accordingly, and a supportive treatment should be given. Also, prophylactics should be given before further administrations. For acute infusion reactions (including cytokine release syndrome, angioedema, anaphylactic shock, allergic reactions, please refer to terms and criteria of NCI CTC AE v4.03), their relevant symptoms and signs usually occur during drug infusion or shortly after infusion, and usually disappear within 24 h after the infusion is completed. The signs and symptoms include: allergic reaction/hypersensitivity reaction (including drug-induced fever), coughing, chills, rigor, dizziness, headache, fatigue (weakness, somnolence), rash/peeling skin, pruritus/itching, arthralgia, myalgia, hypotension/hypertension, nausea, vomiting, diaphoresis, tachycardia, cancer pain, urticaria, dyspnea (shortness of breath), or bronchospasms. Any Grade 3 or 4 infusion reactions must be reported to the sponsor within 24 hours, and should be reported as SAEs if the criteria for SAE are met.

Management of allergic reactions should be based on the medical practice and guidelines of the study center. The treatment recommendations for infusion reactions are shown below for reference.

Table 9-1. Treatment recommendations for infusion reactions

CTCAE Grade	Clinical Symptoms	Clinical Management	SHR-1210 Treatment
Grade 1 (mild)	Mild and transient reactions;	Bedside observation and close monitoring until recovery. (Prophylactics are recommended for subsequent infusion: diphenhydramine 50 mg or equivalent, and/or acetaminophen 325-1000 mg, at least 30 minutes prior to SHR-1210 administration)	Continue

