Grade 2 (moderate)	Moderate reactions requiring treatment or interruption; rapidly resolve after symptomatic treatment (such as antihistamines, non-steroidal antiphlogistics, anesthetics, bronchodilators, intravenous fluids, etc.)	Intravenous drip of normal saline, 50 mg of diphenhydramine IV or equivalent and/or 325-1000 mg of acetaminophen; Bedside observation and close monitoring until recovery. Corticosteroids or bronchodilators can be considered based on clinical needs; The amount of study drug infused should be recorded in the original medical record; Prophylactics are recommended for subsequent infusion: diphenhydramine 50 mg or equivalent, and/or acetaminophen 325-1000 mg, at least 30 minutes prior to SHR-1210 administration. Use corticosteroids (equivalent to 25 mg of hydrocortisone) when necessary.	Interrupt. Re-administer at 50% of the initial rate after symptoms resolve. If no reaction occurs within 30 min, restore the original infusion rate (100%). Closely monitor. If the symptoms recur, the administration of the current SHR-1210 dose will be discontinued.
Grade \geq 3 (severe)	Grade 3: Severe reactions with no rapid resolution after intervention and/or treatment interruption; symptom recurrence after resolution; sequelae requiring hospitalization. Grade 4: life-threatening	Immediately discontinue SHR-1210; Administer normal saline by intravenous infusion. 
 Bronchodilators are recommended: 0.2-1 mg of subcutaneous 1:1000 adrenaline injection or slow intravenous injection of 1:10000 adrenaline solution 0.1-0.25 mg, and/or intravenous diphenhydramine 50 mg plus methylprednisolone 100 mg or equivalent if necessary; Based on the guidelines for anaphylaxis of the study center; Bedside observation and close monitoring until recovery.	Permanently discontinue.

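### Section 6.4 requires SHR-1210 to be stopped for good after an injection reaction only at Grade 4, Table 9-1 from Grade 3, and nothing says which prevails

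*Protocol*

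**What the plan says.** Three sections of the protocol deal with SHR-1210 after an infusion reaction.

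- **Section 6.4 (Dose Modification)** lists the events after which SHR-1210 must be stopped permanently. The entry for this type of event is in the run "other Grade 4 immune-related toxicities (except for hypothyroidism), Grade 4 injection reactions". The same sentence sets the threshold for pneumonitis and recurrent bilirubin elevation at Grade 3 or above.
- **Section 9.2, Table 9-1** has a single row for Grade 3 and above. It describes "Grade 3: Severe reactions with no rapid resolution after intervention and/or treatment interruption", instructs the site to "Immediately discontinue SHR-1210", and gives permanent discontinuation as the SHR-1210 action. The text above the table bases management on the study centre's own practice and guidelines and adds: "The treatment recommendations for infusion reactions are shown below for reference".
- **Sections 8.6 and 9.2 (running text)** have the infusion slowed or interrupted as the situation requires. Section 8.6 continues "In addition, prophylactics should be given before further administration" and Section 9.2 "Also, prophylactics should be given before further administrations". Neither sentence names a grade.

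Section 6.4 does not refer to Table 9-1, and Section 9.2 does not refer to Section 6.4.

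**The concern.** A rule for permanently stopping an antibody after a severe reaction should have one threshold, and this protocol has two. An investigator could reasonably treat Section 6.4 as the binding dose rule and Table 9-1 as advice, because the protocol presents the table as reference material. On that reading a Grade 3 reaction does not require a permanent stop, and the ungraded prophylaxis sentences describe how to give the next dose.

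What is at stake is the safety of the individual subject: SHR-1210 could be given again after a reaction that Table 9-1 says should end it. The other reading is that the table governs. Two sites could handle the same reaction differently and both claim to have followed the protocol.

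**Working it through.** The plan gives no figure on this point to reproduce. The check is a comparison of the texts, followed by a bound on how often the situation could arise.

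**1. The rules by grade**

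| Reaction grade | Section 6.4 permanent-stop list | Table 9-1 | Prophylaxis sentences in 8.6 and 9.2 |
|---|---|---|---|
| 1 | not listed | continue | apply |
| 2 | not listed | interrupt, restart at half rate | apply |
| 3 | not listed | permanent stop | apply (no grade stated) |
| 4 | permanent stop | permanent stop | apply (no grade stated) |

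The two rules differ at Grade 3. They can be obeyed together, since stopping at Grade 3 breaches nothing in Section 6.4. The defect is that Section 6.4 alone does not require it.

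**2. Is it the same event?** Section 6.4 says injection reactions and Table 9-1 says infusion reactions. Section 6.1.1 gives, for SHR-1210, "Route of Administration: Intravenous injection", and the protocol defines no separate class of injection reaction, so I read them as the same event. If they are not, Section 6.4 does not name infusion reactions at all and the remedy is unchanged.

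**3. Does Section 6.4 offer a way back to dosing at Grade 3?** Its dose-modification table interrupts both drugs for Grade 3 non-hematologic toxicity and allows resumption at Grade 1 or below; the stated discontinuation criterion is an SHR-1210 interruption beyond 12 weeks. That row is headed as toxicity related to both drugs, so it is unclear whether it covers a reaction to SHR-1210 alone. The finding does not depend on it.

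**4. How often could it happen?** The inputs are the phase I monotherapy tables in Section 1.7.1 and the planned sample sizes in Section 13.1. The table headings show N = 67, but the percentages use 87 subjects (67/87 = 77.0%; 1/87 = 1.1%).

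- Infusion reaction or anaphylaxis in the table of Grade 3 or greater events: none, taken as 0 of 87.
- Exact one-sided 95% upper bound: 1 − 0.05^(1/87) = 0.0338, or 3.4%.
- Two-sided 95% Clopper-Pearson upper limit: 1 − 0.025^(1/87) = 0.0415, or 4.2%.
- Planned subjects: 40 + 174 = 214 to 60 + 174 = 234.
- Expected number with a Grade ≥ 3 reaction at the one-sided bound: 0.0338 × 214 = 7.2 to 0.0338 × 234 = 7.9. At the two-sided limit: 8.9 to 9.7.
- Anaphylaxis of any grade, from the treatment-related table: 1 of 87, or 1.1%, exact 95% CI 0.03% to 6.2%. It does not appear in the Grade 3 or greater table.

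The documents do not say what share of such subjects would be re-dosed. Under assumed shares, at the one-sided bound:

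| Assumed share re-dosed | Subjects re-dosed (N = 214 to 234) |
|---|---|
| 10% | 0.7 to 0.8 |
| 50% | 3.6 to 4.0 |
| 100% | 7.2 to 7.9 |

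The lower end is zero in every row.

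**The case against.** The best defence is that the protocol already contains the safe instruction. Section 9.2 is the section written for infusion reactions, and a site treating one would look there. Within Table 9-1, prophylaxis for later infusions appears only in the Grade 1 and Grade 2 rows, so Section 9.2 read as a whole does not invite re-dosing at Grade 3. Section 6.4 never says that a Grade 3 reaction may be rechallenged; that it requires the stop only at Grade 4 is an inference from its list. A mandatory stop at Grade 4 with a recommended stop at Grade 3 would also be a coherent two-tier rule.

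There are further safeguards. Section 8.5 makes a Grade ≥ 3 infusion reaction an event of special interest, and Section 9.2 requires Grade 3 and 4 reactions to reach the sponsor within 24 hours. Section 8.6 adds "All Grade 3 or 4 infusion reactions should be reported in accordance with SAE reporting procedures". With dosing every two weeks, the sponsor should normally know before the next dose. Sections 8.7 and 9.1 end treatment for other immune-related reactions at Grade 3, which may cover some cases, and Section 5.3.1 withdraws subjects with intolerable toxicity.

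Most of this stands, and it makes re-dosing less likely. It does not settle the threshold. Reporting informs the sponsor but sets no stopping rule, intolerable toxicity carries no grade, and the prophylaxis sentence in Section 8.6 has no table beside it to limit it. If a two-tier rule was intended, the protocol does not say so.

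**Conclusion.** The concern holds. The protocol gives two thresholds for permanently stopping SHR-1210 after an infusion reaction, they differ at Grade 3, and no text sets an order of precedence. It should be fixed on patient-safety grounds.

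The likely number affected is small: between zero and about 8 subjects with a Grade ≥ 3 reaction at the one-sided bound (about 10 at the two-sided limit), of whom an unknown share would be re-dosed. This assumes that absence from the Grade 3 or greater table means no such event occurred, and that the monotherapy rate carries over to the combination with apatinib. The finding itself rests on the wording and not on these figures. No effect on the objective response rate is claimed.

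**What to change.** - **Section 6.4:** replace the Grade 4 injection-reaction entry with Grade ≥ 3 infusion reactions and a reference to Table 9-1.
- **Section 9.2:** add one sentence making permanent discontinuation in the Grade ≥ 3 row of Table 9-1 mandatory. Leave the Grade 1 and Grade 2 rows as recommendations, so that discretion to slow or interrupt the infusion is kept.
- **Sections 8.6 and 9.2:** limit the sentence on prophylaxis before further dosing to Grade 1 and Grade 2 reactions.

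This adopts the threshold already in Table 9-1 and used for the event of special interest in Section 8.5. The cost is one changed phrase, one added sentence, two grade limits and a letter to sites, with no new procedures. The downside is that a few subjects with a Grade 3 reaction lose the option of SHR-1210 rechallenge. Section 6.4 lets them continue apatinib alone after recovery if the investigator judges that they benefit.

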6.5 Drug Management, Dispensation and Return

The management, dispensing and return of the study drugs of this study are in the charge of designated staff. The investigator must ensure that all the study drugs are only used for the subjects participating in this clinical study. The dosage and administration should follow the study protocol. The remaining or expired drugs should be returned to the sponsor. The study drugs should not be transferred to any non-clinical study participant.

The study drugs should be stored according to the drug storage conditions detailed in the drug information. The drug receipt forms must be signed by two people during drug dispensation. The form is in duplicate copies, of which one is for the study center and the other is for the sponsor. Remaining drugs and empty boxes will be retrieved at the end of the study and a retrieval form will also be signed by both parties. The dispensation and return of every drug should be immediately documented on designated forms.

The clinical research associate (CRA) is responsible for monitoring the supply, usage, and storage of the study drugs, and the management of remaining products.

6.6 Concomitant Medications

6.6.1 Medications that are prohibited during the study and medications that should be used with caution

Drugs that may have drug-drug interactions with apatinib:

In vitro studies have shown that apatinib is prominently metabolized by the liver P450 enzyme CYP3A4. Apatinib has a strong inhibitory effect on CYP3A4 and CYP2C9, and has a moderate inhibitory effect on CYP2C19. CYP3A4 inducers (dexamethasone, carbamazepine, rifampicin and phenobarbital) and inhibitors (ketoconazole, itraconazole, erythromycin and clarithromycin), CYP3A4 substrates (simvastatin, cyclosporine and pimozide), and other drugs metabolized via CYP3A4 (such as benzodiazepines, dihydropyridine, calcium ion antagonist and HMG-CoA reductase inhibitors) should be used with caution during the treatment. Omeprazole should be used with caution during the treatment (except when omeprazole must be used to treat serious adverse drug reactions).

The substrates of CYP2C9 and CYP2C19 should be used with caution, as shown in the table below.

P450 enzyme	Substrate
CYP2C9	Diclofenac, phenytoin, piroxicam, S-warfarin, and tolbutamide
CYP2C19	Diazepam, imipramine, lansoprazole, and S-mephenytoin

Drugs that prolong the QT interval of the heart

As tinib drugs may cause toxicities of prolonged QT interval in clinical applications, drugs that may prolong the QT interval should be used with caution during the study. These mainly include, but are not limited to, the following categories of drugs:

- Antibiotics: fluoroquinolones: sparfloxacin, gatifloxacin, levofloxacin, moxifloxacin, ofloxacin, ciprofloxacin; macrolides: erythromycin, clarithromycin, telithromycin, azithromycin, roxithromycin, and metronidazole
- Antiarrhythmics: quinidine, procainamide, disopyramide, flecainide, propafenone, amiodarone, dronedarone, sotalol, dofetilide, and ibutilide
- Drugs used to relieve angina pectoris: ranolazine, ivabradine
- Antipsychotics: risperidone, fluphenazine, droperidol, haloperidol, thioridazine, pimozide, olanzapine, and clozapine

- Antifungal drugs: voriconazole, posaconazole
- Antimalarial drugs: mefloquine, chloroquine
- Antihistamines: terfenadine, astemizole, hydroxyzine
- Gastrointestinal drugs: antiemetics: ondansetron, granisetron, dolasetron, droperidol (0.625 to 1.25 mg may be a safe dose), hydroxyzine; prokinetics: cisapride, domperidone, metoclopramide
- Antidepressants: amitriptyline, imipramine, clomipramine, dosulepin, and doxepin

CYP3A4 substrates prohibited during the study (drugs with narrow safety windows and may cause serious adverse reactions when their metabolism is affected) include but are not limited to:

- Hypoglycemic agents: tolbutamide, chlorpropamide
- Ergot derivatives: dihydroergotamine, ergometrine, ergotamine, methyl ergometrine (potential risk of ergot poisoning, including severe vasospasm leading to peripheral and cerebral ischemia)
- Antipsychotic: pimozide (can potentially increase the risk of prolonged QT interval)
- Antiarrhythmics: amiodarone (prohibited within 6 months prior to randomization), bepridil, flecainide, lidocaine, mexiletine, quinidine, and propafenone
- Immunomodulators: cyclosporine, tacrolimus, sirolimus (may potentially increase the risk of nephrotoxicity and neurotoxicity)
- Miscellaneous: quetiapine, risperidone, clozapine, tomoxetine hydrochloride

If warfarin is used for anticoagulation during the study, a reduced dose should be considered with its use being monitored closely, and the use of the study drugs should be discontinued if necessary.

During the treatment period, anti-tumor drugs and adjuvant drugs related to tumor treatment, such as anti-tumor traditional Chinese medicine (see Appendix I for a detailed list), immunological agents, etc., should be discontinued.

6.6.2 Drugs and treatments that may be used as appropriate during the study:

In Stage I, for subjects enrolled in the tolerability observation study, except that the subjects experiencing hypertension, rash, diarrhea, nausea and vomiting can be given symptomatic treatments, all other adverse reactions with no clinically significant toxicity occurring during the tolerability observation period (Cycle 1 of drug administration) will not be treated in principle, so as to observe the possible adverse effects and their extent/reversibility of the study drugs. However, in the event of a clinically significant toxicity as specified in the protocol, the treatment should be interrupted and a proactive approach should be used to manage the event. Used medications should be recorded on the eCRF. For subjects experiencing clinically significant toxicity, the treatment can be resumed at the original dose (when the original dose is the lowest dose) or the nearest lower level after the toxicity returns to Grade ≤ 1 after management.

In other cases, the subjects should be given an optimal supportive care during the treatment. Comorbidities and various adverse reactions, especially immune-related adverse reactions, should be actively treated.

Subjects can receive bisphosphonate for the treatment of bone metastases. If systemic or local analgesia is not effective in controlling painful lesions of bone metastases, a small area of palliative radiotherapy (the area of the radiotherapy must be $< 5\%$ of the bone marrow region, and the percent bone marrow content in human skeleton is shown in the figure of **Appendix VI**) is allowed.

Palliative treatment for lesions outside the lungs and liver is allowed during the study (when the treatment of the subjects is needed to improve symptoms upon the onset of PD), including the treatments for pleural effusion, ascites, pericardial effusion, and radiotherapy for brain lesions. During such treatment, the study drugs should be interrupted until the end of the recovery period of palliative treatment.

All concomitant treatments and medications used within 30 days prior to the first dose and during the study should be documented in the eCRF in strict accordance with the GCP regulations. Subjects will be closely monitored if adverse reactions occur, and active symptomatic treatment will be given if necessary. The drugs used will be documented and described in the CRFs. Once the study treatment is interrupted, only the concomitant medication and treatment used to solve new or unresolved treatment-related AEs will be recorded.

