3.1.1 Definition of clinically significant toxicity

1. Grade 4 hematological toxicity or Grade ≥ 3 thrombocytopenia with hemorrhage, Grade ≥ 3 neutropenia with fever and infection;
2. Grade ≥ 3 non-hematological toxicity (except for abnormal laboratory test parameters), hypertension, rash, diarrhea, nausea, and vomiting that cannot be controlled after symptomatic treatment;
3. Grade ≥ 3 abnormal laboratory test parameters that lead to medical intervention, hospitalization, or lasting for ≥ 7 days;
4. SHR-1210 interruption for > 14 days due to relevant toxicity (delayed administration in Cycle 1 or Cycle 2);
5. Apatinib interruption for > 7 days due to relevant toxicity.

3.1.2 Definition of subjects with incomplete tolerance evaluation:

During the observation period of tolerability, the dose of SHR-1210 is < 90% of the prescribed dose due to non-clinically significant toxicity (such as injection reactions).

Subjects who do not complete the tolerability evaluation will not be included in the overall number of subjects undergoing tolerability evaluations, and each dose group is required to have ≥ 10 subjects for the tolerability observation.

Exemption: If ≥ 7 subjects in a dose group do not develop clinically significant toxicity during the tolerability observation period, the dose group is considered to be tolerable and no new subjects will be enrolled into this dose group.

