3.1.3 Follow-up treatment of subjects with clinically significant toxicity

In the observation period of tolerability, the subjects with clinically significant toxicity may receive subsequent combination therapy of SHR-1210 and apatinib based on the investigator's judgment after they have recovered from toxicity: interrupt, reduce (for subjects using 500 mg/d or 375 mg/d apatinib) or discontinue apatinib administration according to the dose modification principles, or discontinue the treatment. Subjects will also be followed up and their data will be collected according to the study procedure.

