		Grade 3	No	Yes	Until the toxicity returns to Grade ≤ 2	Resume at original dose	Two episodes of Grade 4 hematological toxicity
		Grade 4	Yes	Yes	Until the toxicity returns to Grade ≤ 2	Dose reduction or modification of method of administration	
	Non-hematologic toxicity	Grade 1	No	No	—	—	—
		Grade 2 (last for ≥ 7 d)	Yes	Yes	Until the toxicity returns to Grade ≤ 1	Resume at original dose	SHR-1210 interruption for more than 12 weeks
		Grade 3	Yes	Yes	Until the toxicity returns to Grade ≤ 1	Dose reduction or modification of method of administration	
Toxicity related to SHR-1210	Reactive capillary endothelial proliferation	Grade 3	Yes	No	Until the toxicity returns to Grade ≤ 2	Resume at original dose	SHR-1210 interruption for more than 12 weeks

Treatment-Related Toxicity		Grade	Whether to Interrupt Treatment		Criteria for Resuming	Dose Modification Method	Criteria for Discontinuation
			SHR-1210	Apatinib			
Apatinib-Related Toxicities	Hypertension	Grade 3 (after corrective treatment)	No	Yes	Wait until blood pressure returns to within 140/90 mmHg	Dose reduction or modification of method of administration	Subjects with persistent Grade 3 hypertension after the best corrective treatment and the modification of method of administration of apatinib
	Proteinuria (without significant increase in blood creatinine)	Grade 3 (24 h urine protein quantification)	No	Yes	Until the toxicity returns to Grade ≤ 2	Dose reduction or modification of method of administration	Subjects with persistent Grade 3 proteinuria after the best corrective treatment and the modification of method of administration of apatinib
	Hand-and-foot syndrome	Grade 3	No	Yes	Until the toxicity returns to Grade ≤ 1	Dose reduction or modification of method of administration	Subjects with persistent Grade 3 hand-and-foot syndrome after the best corrective treatment and the modification of method of administration of apatinib
	Headache	Grade 2 (last for ≥ 7 d) or Grade 3	No	Yes	Until the toxicity returns to Grade ≤ 1	Dose reduction or modification of method of administration	Apatinib interruption for more than 28 days

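### For Stage I subjects with clinically significant toxicity, Protocol 6.6.2 conflicts with the 6.4 rules that 3.1.3 applies to the same subjects, on recovery grade and apatinib resumption, with no precedence stated

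*Protocol*

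**What the plan says.** Protocol 6.6.2 deals with subjects in the Stage I tolerability observation. It states that "in the event of a clinically significant toxicity as specified in the protocol, the treatment should be interrupted". It adds that "the treatment can be resumed at the original dose (when the original dose is the lowest dose) or the nearest lower level after the toxicity" has recovered, the recovery condition in full being "after the toxicity returns to Grade ≤ 1 after management". That is the original dose if it is the lowest dose, otherwise one level down. The same recovery grade applies to every qualifying toxicity, and no drug is named.

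Protocol 3.1.3 covers the same subjects in the same period. It leaves further combination treatment to the investigator's judgment after recovery. Its options are to interrupt apatinib, or to "reduce (for subjects using 500 mg/d or 375 mg/d apatinib) or discontinue apatinib administration according to the dose modification principles". Those principles are in Section 6.4.

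Section 6.4 has text and a table. The text limits dose reduction to the 500 and 375 mg groups and defines two successive schedule changes. After an apatinib-related reaction it lets the investigator choose among the original dose, a reduction, a changed schedule or stopping. The table sets the rule toxicity by toxicity. Its Grade 3 and Grade 4 hematologic rows both carry the recovery criterion "Until the toxicity returns to Grade ≤ 2". The Grade 3 row then says "Resume at original dose". The Grade 4 hematologic, Grade 3 non-hematologic and apatinib-related rows say "Dose reduction or modification of method of administration".

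The toxicity definition in 3.1.1 includes "Grade 4 hematological toxicity or Grade ≥ 3 thrombocytopenia with hemorrhage, Grade ≥ 3 neutropenia with fever and infection", so subjects can qualify through either hematologic row.

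**The concern.** These subjects have just met the study's toxicity criterion, and the protocol gives two sets of instructions for treating them again. Depending on the section a site follows, the subject may restart at a different grade of residual toxicity and on a different amount of apatinib. A site that follows one section may be recorded as deviating from the other.

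The consequences go beyond Stage I. SAP Section 5 pools the Stage I 250 mg subjects with Cohorts 1 and 3, or with Cohort 2, for all efficacy and safety analyses. Relative dose intensity (SAP 5.1.3 and 5.4.1), adverse events leading to interruption or dose reduction (5.4.3) and deviation classification (5.2.7) all depend on what was done. Deviation classification in turn can affect membership of the per-protocol set (5.1.1).

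**Working it through.** The plan states no figure to reproduce. The check compares the 6.4 table with 6.6.2, which always requires Grade 1 or lower and then gives the original dose at 250 mg and the nearest lower level at 375 or 500 mg.

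| Toxicity | 6.4 table: recovery | 6.4 table: interrupted | 6.4 table: apatinib on resumption | Difference from 6.6.2 |
|---|---|---|---|---|
| Qualifying Grade 3 hematologic (neutropenia complicated by fever and infection; thrombocytopenia with bleeding) | ≤ 2 | Apatinib only | Original dose | Recovery grade; dosing at 375 and 500 mg; drug unclear |
| Grade 4 hematologic | ≤ 2 | Both | Reduction or changed schedule | Recovery grade; dosing at 250 mg |
| Grade 3 non-hematologic, general row | ≤ 1 | Both | Reduction or changed schedule | Dosing at 250 mg |
| Grade 3 proteinuria, if it qualifies | ≤ 2 | Apatinib only | Reduction or changed schedule | Recovery grade; dosing at 250 mg by the table; drug unclear |
| Grade 3 hypertension, if uncontrolled | Within 140/90 mmHg | Apatinib only | Reduction or changed schedule | Criterion in other terms; dosing at 250 mg by the table; drug unclear |
| Grade 3 hand-and-foot syndrome | ≤ 1 | Apatinib only | Reduction or changed schedule | Dosing at 250 mg by the table; drug unclear |

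The 250 mg entries follow because 6.4 confines reduction to the two higher groups, which leaves a changed schedule as the table's only option.

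Section 6.4 also disagrees with its own table. For apatinib-related reactions its text lists the original dose, which those rows omit. In the other direction, a paragraph after the table asks for a reduction or changed schedule once Grade 3 or higher treatment-related toxicity has resolved, while the Grade 3 hematologic row restores the original dose.

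**Size at 250 mg.** The first schedule change is 5 days on, 2 days off:

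- Average dose: 250 × 5/7 = 178.6, about 179 mg/day, against 250 mg/day.
- Difference: 1 − 5/7 = 28.6%, about 29% lower.

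**Effect on relative dose intensity.** Suppose a fraction f of the apatinib period is on that schedule, the rest is daily, off days count as zero dose, and nothing else is missed. Relative dose intensity is then 100 × (1 − 2f/7). At f = 1 it is 71.4%. It reaches the SAP's 80% category boundary at f = 0.20 × 7/2 = 0.70. A subject on the schedule for more than 70% of the period is therefore classed below 80%; the same subject on uninterrupted daily dosing is at 100%.

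**The case against.** **The Stage I dose decision looks already taken.** Protocol 3.1 reports that 250 mg was selected for Stage II from the Stage I tolerability results, and the SAP has groups only for 250 and 375 mg. The 6.6.2 rule concerns the Stage I tolerability cohort, so rewording it may change few or no future treatments. This stands. It limits the prospective effect, but not the need to know which rule was applied to subjects already treated.

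**6.6.2 could be a stricter special rule.** A site that waits for Grade 1 has also passed Grade 2. That is true, but a site that follows the table to Grade 2 breaches 6.6.2. Nothing says that 6.6.2 overrides 6.4, and 3.1.3 sends the same subjects to 6.4.

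**6.4 leaves room for judgment.** Its text offers the original dose after apatinib-related reactions, so a reader who infers that 6.4 as a whole forces a changed schedule at 250 mg in every row goes too far. Section 6.4 also describes intermittent dosing as keeping the original dose, so the 250 mg wording in 6.6.2 might refer to the daily amount and leave the schedule open. But 6.6.2 does not mention schedule, and a site may fairly read it as permitting unchanged daily dosing. Neither point reaches the hematologic recovery grade, or the 375 and 500 mg conflict between 6.6.2 and the table.

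**6.6.2 names no drug.** A reader might infer that it orders both drugs stopped. The documents do not establish this: 3.1.3 speaks of apatinib, and a lower dose level can only mean apatinib because SHR-1210 is fixed at 200 mg. This is an ambiguity, not a proven contradiction.

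**Some examples are conditional.** Under 3.1.1, hypertension must be uncontrolled after symptomatic treatment. Proteinuria, as a laboratory abnormality, must lead to intervention or hospitalization or last at least 7 days.

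**Conclusion.** The conflict is real. It is firmest for the hematologic recovery grade and for apatinib dosing after Grade 4 or qualifying Grade 3 hematologic toxicity. The general Grade 3 non-hematologic row conflicts only on dosing at 250 mg. Not every toxicity shows all three differences. The drug-interruption point is a matter for clarification.

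At 250 mg the first changed schedule gives 29% less apatinib per day than daily dosing, assuming that the site takes 6.6.2 to mean daily dosing.

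Three larger readings are tempting, and the documents do not support them:

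- **A 50% loss of dose.** Alternate-day dosing averages 125 mg/day, but 6.4 makes it a later re-modification, not the first resumption.
- **Up to 30% of a dose group affected.** The limit of < 0.33 allows 3 of 10 toxicity cases in a tolerable group. That counts neither subjects for whom the rules differ nor cases in a group judged intolerable.
- **A changed tolerability decision through the interruption criteria.** These subjects already count as toxicity cases, and the decision uses a proportion of subjects, so the proportion does not move.

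What can change is later exposure, dose-intensity and interruption summaries, and deviation classification. No effect on the Stage II response rate is shown.

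**What to change.** The sponsor must reconcile Protocol 3.1.3, 6.4 (text and table) and 6.6.2. For each qualifying toxicity there should be one recovery criterion, one resumption rule and one statement of which drug is interrupted. Alternatively, the protocol should state which section takes precedence. The disagreement between the 6.4 text and its own table should be settled at the same time. The choice of rule is clinical, and none is proposed here.

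If Stage I tolerability observation is complete, a clarification note should record which rule was applied to each affected subject, so that dose intensity and deviations can be judged against it. The cost is protocol wording or a note to file, plus a short listing. No new data collection, sample size or analysis method is involved.
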